- sCR rate, defined as the percentage of subjects achieving CR in addition to having a normal free light chain (FLC) ratio and an absence of clonal cells in bone marrow by immunohistochemistry, immunofluorescence, 2-4 color flow cytometry
- Overall response rate (ORR), defined as the proportion of subjects who achieve PR or better, according to the IMWG criteria, during or after the study treatment.
- Proportion of subjects who achieve VGPR or better, defined as the proportion of subjects achieving VGPR and CR (including sCR) according to the IMWG criteria during or after the study treatment at the time of data cut-off.
- Time to response, defined as the time between the randomization and the first efficacy evaluation that the subject has met all criteria for PR or better. For subjects without response, data will be censored either at the date of progressive disease or, in the absence of progressive disease, at the last disease evaluation before the start of subsequent anti-myeloma therapy.
- Duration of response, calculated from the date of initial documentation of a response (PR or better) to the date of first documented evidence of progressive disease, as defined in the IMWG criteria. For subjects who have not progressed, data will be censored at the last disease evaluation before the start of any subsequent anti-myeloma therapy.
- To evaluate clinical efficacy of DRd in high risk molecular subgroups compared to Rd alone.
- To evaluate the impact of DRd compared to Rd on patient-reported perception of global health.

PHARMACOKINETIC AND IMMUNOGENICITY EVALUATIONS

Samples to assess both the serum concentration (pharmacokinetics) of daratumumab and the generation of antibodies to daratumumab and rHuPH20 (immunogenicity) will be obtained in the D-Rd group according to the Time and Events Schedule. Following amendment 8, subjects in Treatment Arm B who continue to receive daratumumab IV no longer require pharmacokinetic and immunogenicity sampling, however subjects in Treatment Arm B who switch to daratumumab SC will require pharmacokinetic and immunogenicity samples as specified in the Time and Events Schedule.

BIOMARKER EVALUATIONS

Bone marrow aspirates will be collected at screening and following treatment as outlined in the Time and Events Schedule. Baseline bone marrow aspirate samples will be subjected to DNA and RNA sequencing in order to classify subjects into high-risk molecular subgroups and to establish the myeloma clone for MRD monitoring.

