- OS, measured from the date of randomization to the date of the subject's death. If the subject is alive or the vital status is unknown, then the subject's data will be censored at the date the subject was last known to be alive.
- sCR rate, defined as the percentage of subjects achieving CR in addition to having a normal FLC ratio and an absence of clonal cells in bone marrow by immunohistochemistry, immunofluorescence, 2-4 color flow cytometry.
- Time to next treatment, defined as the time from randomization to the start of the next-line treatment.
- Overall response rate (ORR), defined as the proportion of subjects who achieve PR or better, according to the IMWG criteria, during or after the study treatment.

- Proportion of subjects who achieve VGPR or better, defined as the proportion of subjects achieving VGPR and CR (including sCR) according to the IMWG criteria during or after the study treatment at the time of data cut-off.
- Time to response, defined as the time between the randomization and the first efficacy evaluation that the subject has met all criteria for CR or PR. For subjects without response (CR/PR), data will be censored either at the date of progressive disease or, in the absence of progressive disease, at the last disease evaluation before the start of subsequent anti-myeloma therapy.
- Duration of response, calculated from the date of initial documentation of a response (PR or better) to the date of first documented evidence of progressive disease, as defined in the IMWG criteria. For subjects who have not progressed, data will be censored at the last disease evaluation before the start of any subsequent anti-myeloma therapy.
- To evaluate clinical efficacy of DRd in high risk molecular subgroups compared to Rd alone.
- To evaluate the impact of DRd compared to Rd on patient-reported perception of global health.

Exploratory Endpoints

- Biomarkers predictive of response or resistance to daratumumab.
- Durability of MRD negativity.

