11.1. Subject Information

The primary analysis population will be the intent-to-treat (ITT) population, which will include all randomized subjects. Safety will be evaluated for the population of all treated subjects. The pharmacokinetic analyses will be performed on the pharmacokinetic evaluable population. Continuous variables will be summarized using descriptive statistics such as mean, standard deviation, and range. Categorical variables will be summarized using frequency tables. For time-to-event variables, the Kaplan-Meier method will be used for descriptive summaries.

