2.9. Analysis Sets

The following analysis sets are defined.

- Intent-to-treat (ITT): defined as subjects who have been randomly assigned to the DRd or Rd group. Analyses of demographics, baseline characteristics and efficacy endpoints will be primarily analyzed based on this population.
- Safety population: defined as subjects who have received at least 1 administration of any study treatment (partial or complete). This population will be used for all safety analyses. The safety analyses grouping will be according to treatment actually received.
- Response-evaluable: defined as subjects who have a confirmed diagnosis of multiple
 myeloma and measurable disease at baseline or screening visit. In addition, subjects must
 have received at least one administration of study treatment and have adequate postbaseline disease assessments. Measurable disease is defined as follows:
 - IgG myeloma: Serum monoclonal paraprotein (M-protein) level ≥1.0 g/dL or urine M-protein level ≥200 mg/24 hours; or
 - IgA, IgD, IgE or IgM multiple myeloma: serum M-protein level ≥0.5 g/dL or urine M-protein level ≥200 mg/24 hours; or
 - Light chain multiple myeloma without measurable disease in serum or urine: Serum immunoglobulin free light chain (FLC) level ≥10 mg/dL and abnormal serum immunoglobulin kappa lambda free light chain ratio.

This population will be used as sensitivity analyses for selective response-related secondary endpoints such as CR or better rate.

- Per-protocol (PP) population: defined as subjects who are randomized and meet all eligibility criteria.
- Pharmacokinetics-evaluable: is defined as subjects assigned to DRd group who received at least 1 administration of daratumumab and have at least 1 pharmacokinetic sample concentration value after the first infusion. All pharmacokinetics analyses are based on the pharmacokinetic evaluable population.
- Immune response-evaluable: is defined as subjects assigned to DRd group who have at least 1 immunogenicity sample obtained after their first daratumumab administration.
- Molecular genetic evaluable: defined as subjects who meet one of the following biomarker criteria for risk assessment based on the next generation sequencing (NGS) data:
 - Standard risk: subjects that are negative (=molecular aberration absent) for all del17p, t(14;16), t(4;14).
 - High risk: subjects that are positive (=molecular aberration present) for any of del17p, t(14;16), t(4;14).

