4.3.10. Time to Response

4.3.10.1. Definition

Time to response (i.e., time to first response) is defined as the time between the date of randomization and the first efficacy evaluation that the subject has met all criteria for PR or better based on the computerized algorithm for patients who had PR or better as their best response.

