4.3.10.2. Analysis Methods

For subjects who achieve a confirmed response, descriptive statistics (n, mean, standard deviation, median, and range) will also be provided to summarize time to response, time to VGPR or better response and time to CR or better response.

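### The SAP reports time to response in responders only, whereas the protocol keeps non-responders in with a censoring rule; the by-arm summary is conditional on response and should not be read as a randomized comparison

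*SAP*

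**What the plan says.** The protocol defines the endpoint twice. The synopsis measures time from randomization to the first evaluation meeting all criteria for PR or better, and adds: "For subjects without response, data will be censored either at the date of progressive disease or, in the absence of progressive disease", with the last disease evaluation before subsequent anti-myeloma therapy as the alternative date. Section 9.2.2 repeats the rule, "For subjects without response (CR/PR), data will be censored either at the date of progressive disease or, in the absence of progressive disease", but names the event as CR or PR. Protocol Section 11.1 states: "The primary analysis population will be the intent-to-treat (ITT) population, which will include all randomized subjects". SAP Section 2.9 agrees that "efficacy endpoints will be primarily analyzed based on this population", meaning ITT.

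SAP Section 4.3.10.1 also starts the clock at randomization and uses PR or better by the computerized algorithm, but it defines the variable only "for patients who had PR or better as their best response" and contains no censoring rule. The analysis in Section 4.3.10.2 reads: "For subjects who achieve a confirmed response, descriptive statistics (n, mean, standard deviation, median, and range) will also be provided to summarize time to response", together with time to VGPR or better and time to CR or better. It names no Kaplan-Meier estimate, hazard ratio or test.

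SAP Section 1.1 includes time to response in the list of secondary endpoints on which the two treatment groups are to be compared.

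**The concern.** A rule for censoring non-responders has meaning only if they are in the analysis. The protocol's endpoint therefore concerns how soon randomized subjects respond. The SAP's endpoint concerns how soon responders respond, given that they do. Section 4.3.10 does not mention the departure.

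Response is a post-randomization outcome. The responders in the two arms are not groups formed by randomization, so a difference or a similarity between their medians cannot be attributed to treatment in the usual way. A reader of the study report who sees the two medians side by side, for an endpoint listed for comparison, could take them as a randomized contrast. What is at stake is the interpretation of one descriptive secondary result.

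**Working it through.** **Text comparison.** The documents state no figure for time to response, so there is none to reproduce. The check is whether any other text restores the non-responders.

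- SAP Section 2.8 has a general rule that time-to-event variables measured from randomization are summarized by Kaplan-Meier. Section 4.3.10.1 has already removed everyone without a response, so Kaplan-Meier on that set would still condition on response.
- SAP Attachment 1 plans Kaplan-Meier estimates in the ITT population for time to best response. That is a different endpoint, in an attachment of additional exploratory analyses.
- Protocol Section 11.3 names the endpoints analyzed in the same way as PFS: TTP, PFS2, OS and time to subsequent treatment. Time to response is not among them.
- The SAP follows Amendment INT-4. The protocol's amendment history records that time to response was added at INT-3, so a version lag does not explain the difference.

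None of these passages supplies the protocol-defined analysis.

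**Illustration of size.** All inputs below are assumptions. Let ORR be the proportion of randomized subjects who ever respond. Suppose responders' times are exponential with mean 1.5 cycles in both arms, so that speed among responders is identical. Then:

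- The share of responders who have responded by cycle 2 is 1 − exp(−2/1.5) = 0.736, whatever the ORR.
- The share of all randomized subjects who have responded by cycle 2 is ORR × 0.736.
- Half of all randomized subjects have responded at percentile 0.50/ORR of the responder distribution. The SAP always reports the 50th.

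| Assumed ORR | Responders responding by cycle 2 | Randomized responding by cycle 2 | 0.50/ORR |
|---|---|---|---|
| 50% | 73.6% | 36.8% | 100% |
| 70% | 73.6% | 51.5% | 71.4% |
| 80% | 73.6% | 58.9% | 62.5% |
| 90% | 73.6% | 66.3% | 55.6% |

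A simulation under these assumptions (200 runs, 365 per arm, 28-day visits, non-responders censored with mean 12 cycles) agrees. For Rd vs DRd rates of 80/80, 80/90, 70/90 and 50/90, the mean responder median was about 1.6 to 1.7 cycles in both arms throughout. The share of all randomized subjects responding by cycle 2 was 59% vs 59%, 59% vs 66%, 52% vs 67% and 37% vs 66%. A log-rank test under the protocol's censoring rejected in 6%, 88%, 100% and 100% of runs. On responders only it rejected in about 5% to 7%.

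**How far this reaches in time units.** The time at percentile q is −1.5 × ln(1 − q): 1.04 cycles at the 50th, 1.22 at the 55.6th, 1.47 at the 62.5th and 1.88 at the 71.4th. With assessments every 28 days, all four are first seen at the second visit. Under these assumptions, the reported median would hardly move for ORRs of 70% to 90%. The information lost is the proportion responding by a given time, not a large shift in the median.

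**The case against.** The strongest reply is that this is only a descriptive summary. Section 4.3.10.2 specifies no test, confidence interval or curve. Time to response is not in the testing hierarchy of SAP Section 4.1.1, and protocol Section 11 leaves analytic detail to the SAP. This stands, and it limits the point to one of definition and labelling. It does not remove it: for duration of response both documents say that no formal comparison is made, but neither says so for time to response.

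A second reply is that non-responders are covered elsewhere. A reader might infer that the plan ignores them. It does not: CR or better, VGPR or better and ORR are analyzed in ITT with exact confidence intervals and stratified CMH tests, and all three are in the hierarchy. The log-rank rejections in the simulation reflect the assumed difference in ORR, which those tests already address.

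A third reply is that the word also in Section 4.3.10.2 suggests a lost sentence about another analysis, so this may be a drafting gap and not a settled choice. That is plausible, and it still leaves the section incomplete.

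A reader might also infer that the arms will be formally compared on responders, or that an arm gaining late responders will look slower. The SAP specifies no such comparison. The documents contain no data on the timing of response, and the simulation showed no spurious arm difference in the responder summary. Neither claim is supported.

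**Conclusion.** The mismatch is real but minor. The SAP does not deliver time to response as the protocol defines it, and what it reports by arm is conditional on response. The protocol's definition does not itself say all randomized subjects; that reading rests on its censoring rule together with the ITT population. The primary endpoint, Type I error and the ITT response-rate tests are unaffected. Any size depends on response rates and response speeds that the documents do not give. Over an assumed ORR of 50% to 90%, with equal speed among responders, the proportion of randomized subjects responding by cycle 2 varies from about 37% to 66%, while the responder-only figure stays at about 74%.

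Two smaller points belong with it. Section 9.2.2 says CR or PR where the synopsis says PR or better; the SAP already uses the latter, so no analysis changes. The protocol's own rule treats progression as ordinary censoring, although SAP Attachment 2 (clarification 3.2.2) makes no response assessment after progression. Progression before response is therefore better handled as a competing event.

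**What to change.** In SAP Section 4.3.10, estimate time to first PR or better in the ITT population with non-responders retained. Cumulative incidence by arm is preferable, with progression or death before response as competing events. At minimum, use Kaplan-Meier under the protocol's censoring rule.

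Keep the responder-only descriptives for PR, VGPR and CR as supplementary, labelled as conditional on response and not for between-arm comparison. The protocol defines no time to VGPR or time to CR endpoint, so these need no more than the label. Change the event in protocol Section 9.2.2 to PR or better, to match the synopsis.

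The cost is a few lines of SAP text and one standard analysis of data already collected. The final CSR analysis, which is to update efficacy, can carry it.

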4.3.10.2. Analysis Methods

For subjects who achieve a confirmed response, descriptive statistics (n, mean, standard deviation, median, and range) will also be provided to summarize time to response, time to VGPR or better response and time to CR or better response.

4.3.11. Duration of Response

4.3.11.1. Definition

Duration of response (DOR) is defined for subjects with a confirmed response (PR or better) as the time between first documentation of response and disease progression based on the computerized algorithm, according to IMWG response criteria, or death due to PD, whichever occurs first. Responders without disease progression will be censored at the censoring time point for TTP.

4.3.11.2. Analysis Methods

No formal statistical comparison of DOR between the 2 treatment groups is planned. Analysis of DOR will be based on subjects who achieved a confirmed response of PR or better. Median DOR with 95% CI will be estimated based on the Kaplan-Meier method for each treatment group. The Kaplan-Meier duration of response curve will be plotted by treatment group.

4.4. Subgroup Analysis of Efficacy Endpoints

For assessment of internal consistency and investigation of homogeneity of the treatment effect across subgroups, subgroup analyses of the primary and selected secondary efficacy endpoints will be conducted based on pre-specified subgroups defined in Section 2.10.

A forest plot of subgroup analysis on PFS and selected secondary endpoints (e.g. ORR) will be generated, respectively.

Additionally, the primary endpoint of PFS and secondary endpoint of TTP may be explored by responder vs non-responder for each treatment group.

4.5. Functional Status and Well-being

4.5.1. Definition

Functional status and well-being will be assessed using 2 PRO measures, the EORTC QLQ-C30 and the EQ-5D-5L.

The EORTC QLQ-C30 includes 30 items resulting in 5 functional scales (physical functioning, role functioning, emotional functioning, cognitive functioning, and social functioning), 1 Global Health Status scale, 3 symptom scales (fatigue, nausea and vomiting, and pain), and 6 single items (dyspnea, insomnia, appetite loss, constipation, diarrhea, and financial difficulties). The recall period is 1 week (the past week).

The instrument contains 28 items using a verbal rating scale with 4 response options: "Not at All," "A Little," "Quite a Bit," and "Very Much" (scored 1 to 4). Two additional items use response options (1 to 7): 1 = Very Poor, to 7 = Excellent. All scale and item scores will be linearly transformed to be in the range from 0 to 100 according to the algorithm in EORTC QLQ-C30 scoring manual, version 3.0 (Fayers et al, 2001). A higher score represents a higher ("better") level of functioning, or a higher ("worse") level of symptoms.

The EQ-5D-5L is a generic measure of health status. For purposes of this study, the EQ-5D-5L will be used to generate utility scores for use in cost effective analyses. The EQ-5D-5L is a 5-item questionnaire that assesses 5 domains including mobility, self-care, usual activities, pain/discomfort and anxiety/depression plus a visual analog scale rating "health today" with anchors ranging from 0 (worst imaginable health state) to 100 (best imaginable health state). The scores for the 5 separate questions are categorical and cannot be analyzed as cardinal numbers. However, the scores for the 5 dimensions are used to compute a single utility score ranging from zero (0.0) to 1 (1.0) representing the general health status of the individual (but allows for values less than 0 by UK scoring algorithm).

4.5.2. Analysis Methods

Compliance rates for completion of EORTC QLQ-C30 and EQ-5D-5L at each time point will be generated based on number of expected.

Key PRO endpoints

- EORTC QLQ-C30 global health status/quality of life subscale
- EQ-5D-5L utility score
- EQ-5D-5L visual analog scale (VAS)

The change from baseline at each time point will be summarized descriptively by treatment group.

A distribution based method will be used to define worsening/improvement in scores, i.e., half standard deviation away from the mean score at baseline combining both treatment groups. Time to worsening and time to improvement will be derived. Death due to disease progression will be considered as worsening. Subjects who have not met the definition of worsening/improvement will be censored at the last PRO assessment. Subjects without baseline assessment or post-baseline assessment will be censored at date of randomization.

Time to improvement will be descriptively reported. Time to worsening will be estimated using Kaplan-Meier methods. The hazard ratio for DRd relative to Rd and its associated 95% confidence interval (CI) will be calculated based on the stratified Cox proportional hazards model by the stratification factor at randomization.

A mixed effects model with repeated measures analysis will be conducted estimating change from baseline at each time point between two treatments. ITT subjects who have a baseline value and at least one post-baseline value are included in the analysis. Change from baseline will be fitted to a mixed effects model including subjects as a random effect, and baseline value, treatment group, time in week, treatment-by-time interaction, and stratification factors as fixed effects. Line plot of LS mean of change from baseline with standard error over time will be displayed by treatment arm.

Secondary PRO endpoints

These may include other QLQ-C30 scales:

- functional scales: physical, role, cognitive, emotional, and social
- symptom scales: fatigue, pain, and nausea and vomiting
- single-item score: dyspnea, loss of appetite, insomnia, constipation, diarrhea, and financial difficulties

The change from baseline at each time point may be summarized descriptively by treatment group.

Time to worsening/improvement and mixed effect model analysis, as described for the key PRO endpoints, may be performed as appropriate. Line plot of LS mean of change from baseline with standard error over time may be displayed by treatment arm.

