11.8. Patient Reported Outcomes

EORTC-QLQ-C30 scores will be evaluated for all domains except "financial problems" among subjects with at least one post-baseline assessment and 50% completion of the relevant items for a domain. Descriptive analyses followed by mixed model repeated measures will be used to analyze each domain score. No adjustment for multiple comparisons will be made.

EQ-5D-5L scores will be summarized at each time point.

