4.1. Analysis Specifications

4.1.1. Level of Significance

All statistical hypothesis tests and 95% confidence interval presented will be 2-sided.

The primary hypothesis is to be tested at the 0.05 significance level (overall). The exact significance level at the second interim analysis is to be determined by the observed number of events per the O'Brien-Fleming alpha spending function. Assuming 234 PFS events are observed at the second interim analysis, the alpha to be spent will be 0.0076 (2-sided) for the interim analysis and 0.0476 (2-sided) for the primary PFS analysis (390 PFS events occur). If the observed two-sided p-value is smaller than this significance level as specified above, the superiority of DRd versus Rd with respect to PFS will be established.

If the primary endpoint of PFS is statistically significant, the following secondary endpoints ordered below will be sequentially tested, each with an overall two-sided alpha of 0.05, by utilizing a hierarchical testing approach as proposed by Tang and Geller (1999) that strongly controls Type I error rate:

- 1) CR or better rate
- 2) VGPR or better rate
- 3) MRD negativity rate (10⁻⁵)
- 4) Overall response rate (ORR)
- 5) Overall survival (OS)

These secondary endpoints will be tested at the 2nd IA and the primary PFS analysis. The primary PFS analysis will be skipped if PFS is positive at the 2nd IA. If this is the case, the protocol will be amended to add an analysis for secondary endpoints at a similar timing as the planned primary PFS analysis (note that OS will also be tested at its protocol-specified final analysis). The significance level at the second interim and the primary PFS analyses will be determined by the alpha-spending function specific to endpoints:

- For ORR, VGPR or better rate, CR or better rate, and MRD negativity rate (10⁻⁵), the information fraction is expected to be 80% at the 2nd IA. The O'Brien-Fleming alphaspending function as implemented by the Lan-DeMets method will be used for alphaspending: 0.0244 (two-sided) at the 2nd IA and 0.0428 (two-sided) at the primary PFS analysis.

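### The PRO worsening/improvement threshold in SAP 4.5.2 is set around the pooled baseline mean, not the subject's own baseline

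*SAP*

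**What the plan says.** The rule is in SAP 4.5.2 (Functional Status and Well-being, Analysis Methods). "A distribution based method will be used to define worsening/improvement in scores", and the explanation that follows, introduced by i.e., is "half standard deviation away from the mean score at baseline combining both treatment groups". Next comes "Time to worsening and time to improvement will be derived". Time to worsening gets Kaplan-Meier estimates and a stratified Cox hazard ratio with 95% CI; time to improvement is descriptive.

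The key PRO endpoints are QLQ-C30 global health status, the EQ-5D-5L utility score and the EQ-5D-5L VAS. For the other QLQ-C30 scales and single items, "Time to worsening/improvement and mixed effect model analysis, as described for the key PRO endpoints, may be performed as appropriate".

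Three other statements bear on how the rule should be read:
- Censoring, in the same paragraph of SAP 4.5.2: "Subjects without baseline assessment or post-baseline assessment will be censored at date of randomization".
- Direction of QLQ-C30 scores, SAP 4.5.1: "A higher score represents a higher ('better') level of functioning, or a higher ('worse') level of symptoms".
- Protocol 11.8, which does not mention time to worsening: "Descriptive analyses followed by mixed model repeated measures will be used to analyze each domain score".

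**The concern.** Worsening normally means that a patient has declined from where that patient began. The threshold sentence measures something else: whether a score lies more than half an SD from the average baseline score of all subjects in both arms. A patient who enters with poor global health and stays the same would be an event at the first post-baseline assessment. A patient who enters with excellent health and loses a large amount, but stays above the common cut-off, would not be an event. The SAP does not say how to treat subjects already beyond the cut-off at baseline.

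If programmed that way, time to worsening and time to improvement would partly record starting level rather than change. One of the three scores affected, global health, is the PRO scale that Protocol 9.7 designates as a secondary endpoint.

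**Working it through.** **Reading the text.** The plan states no PRO sample size, power or threshold figure, so there is nothing to reproduce. The possible sources of a within-subject rule are:

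| Place | What it supplies |
|---|---|
| SAP 4.5.2, threshold sentence | Pooled baseline mean and half an SD; applied to scores, not to changes |
| SAP 4.5.2, summaries and mixed model | Change from baseline, but as separate analyses |
| SAP 4.5.2, censoring rule | Needs a baseline for each subject, which a common cut-off would not |
| SAP 2.5 | Which measurement counts as baseline |
| SAP 4.5.1 | Scale direction only |
| Protocol 11.8 | Descriptive summaries and a mixed model only |

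None of them states a within-subject threshold. The censoring rule points towards change from own baseline, but that is inference.

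**Illustration** (assumed mean 55, SD 22, higher is better). The common cut-offs are 55 − 11 = 44 and 55 + 11 = 66. A subject at 40 is already below 44 and counts as worsened with no change. A subject at 90 must lose 90 − 44 = 46 points. Under an own-baseline rule, each would need to fall by 0.5 × 22 = 11 points.

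**Share beyond a cut-off at baseline.** The planned size is 730 (SAP 1.1). Assume normal scores and a baseline PRO for everyone. Then Φ(−0.5) = 0.3085 per side, and 0.3085 × 730 = 225 subjects. Between the cut-offs lie 1 − 2 × 0.3085 = 0.383.

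The share depends on the scale:
- A 13-level 0–100 score (mean 40–70, SD 18–28) gives 24–37% per side.
- A rounded VAS (mean 50–75, SD 15–25) gives 23–40% below and 25–40% above.
- A four-level symptom item with an assumed 60/25/10/5% split over 0/33/67/100 has mean 20 and SD about 29, so the cut-offs are about 5.5 and 34.5. Then 60% start beyond the improvement cut-off and 15% beyond the worsening cut-off.

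The EQ-5D-5L utility was not modelled.

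**Agreement of the two rules at one visit.** Let B be the baseline and F the visit score, in baseline SD units centred on the pooled baseline mean. Assume they are bivariate normal with equal SD, correlation ρ and visit mean δ.
- Literal rule: F ≤ −0.5.
- Own-baseline rule: F − B ≤ −0.5, where F − B has mean δ and variance 2 − 2ρ.

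With δ = 0:

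| ρ | Literal | Own baseline | Both | Flagged without own 0.5 SD drop | Own drop missed |
|---|---|---|---|---|---|
| 0.5 | 0.309 | 0.309 | 0.163 | 1 − 0.163/0.309 = 47% | 47% |
| 0.7 | 0.309 | 0.259 | 0.128 | 59% | 51% |
| 0.9 | 0.309 | 0.132 | 0.059 | 81% | 56% |

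Percentages come from unrounded probabilities. For δ from −0.2 to +0.4 SD, the last two columns range over 42–96% and 42–65%. These are single-visit figures, not error rates for a time-to-first-event endpoint over repeated visits.

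**The case against.** The strongest reply is that nobody would program the literal rule. Worsening is ordinary language for change, the sentence just before concerns change from baseline, and the censoring rule makes sense only if each subject's baseline is used. Much of this stands: own-baseline change was probably intended, and nothing in the documents shows that the literal version was run. But the SAP writes change from baseline explicitly for its other PRO analyses and not here. One sentence points to a common cut-off and another to an own-baseline rule, so two programmers could code different endpoints.

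The second reply is limited consequence, and that also stands. SAP 4.1.1 says "the following secondary endpoints ordered below will be sequentially tested, each with an overall two-sided alpha of 0.05", and no PRO endpoint is in that list. Protocol 11.8 relies on the mixed model. Use on the symptom scales is optional, and their direction can be inferred from SAP 4.5.1, though the rule does not state it.

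A reader might infer that the rule favours an arm or dilutes the hazard ratio. The documents do not support this: the rule is the same in both arms and no PRO parameters are given. Simulations with an assumed +0.3 SD benefit, and no deaths or dropout, gave literal versus own-baseline hazard ratios from 0.65 v 0.20 to 0.65 v 0.71 depending on the correlation model, so no consistent effect can be claimed. They also omit the SAP's rule that death due to progression counts as worsening.

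Nor should one infer that SAP 4.5.2 ignores the subject's baseline altogether. The gap is in the threshold sentence.

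**Conclusion.** The concern holds for the threshold sentence. As written it gives one cut-off per direction and per scale, common to all subjects, and no other part of either document replaces it with a within-subject rule. It would count unchanged low scorers as worsened and miss real declines among high scorers.

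The wording finding needs no assumption. The sizes do: about 31% per side already beyond a cut-off rests on normal scores, and the classification figures rest also on the assumed correlations and mean shifts. All of them apply only if the literal rule is used.

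The effect is confined to supportive PRO time-to-event analyses. PFS, the tested secondary endpoints, the sample size and the mixed model are unaffected. The correction should be made, but it does not threaten the trial's main conclusions.

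**What to change.** Replace the threshold sentence in SAP 4.5.2 with:

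> Worsening (improvement) is a decrease (increase) from the subject's own baseline of at least 0.5 times the pooled baseline SD of that scale, with direction reversed for symptom scales and symptom items.

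Apply it to the key PRO endpoints and to any secondary PRO endpoint analysed this way.

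This can no longer count as pre-specification. SAP version 2.0 is dated 3 October 2018, after the 24 September 2018 clinical cut-off given in Protocol 3.1. The change should therefore be labelled as a clarification made after the cut-off. If the literal rule was already run, report both versions, labelled.

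The cost is one sentence and, only if the literal rule was programmed, one derivation change with a rerun of the affected outputs. If own-baseline change was always used, it is documentation only. No new data are needed.
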